3.0 PARTICIPANT SELECTION

All protocol participants must meet all stated eligibility criteria. Participating sites must have documentation that each eligibility requirement is satisfied prior to subject enrollment. In compliance with CTEP policy, no exceptions to eligibility criteria will be granted under any circumstance.

3.1 Inclusion Criteria

- 3.1.1 Participants (who have been adequately clinically staged by standard clinical guidelines) with primary, untreated, histologically-confirmed, documented invasive squamous cell carcinoma, adenocarcinoma, or adenosquamous carcinoma of the uterine cervix, FIGO stages IB2, IIA, IIB, IIIA, IIIB, and IVA. (Stage IIA tumors must be greater than 4 cm.)
- 3.1.2 HIV-1 infection, documented by any licensed rapid HIV test or HIV enzyme or chemiluminescence immunoassay (E/CIA) test kit at any time prior to study entry and confirmed by a licensed Western blot or a second antibody test by a method other than the initial rapid HIV and/or E/CIA, or by HIV-1 antigen, plasma HIV-1 RNA viral load.

NOTE: The term “licensed” refers to a U.S FDA-approved kit or for sites located in countries other than the United States, a kit that has been certified or licensed by an oversight body within that country and validated internally.

WHO (World Health Organization) and CDC (Centers for Disease Control and Prevention) guidelines mandate that confirmation of the initial test result must use a test that is different from the one used for the initial assessment. A reactive initial rapid test should be confirmed by either another type of rapid assay or an E/CIA that is based on a different antigen preparation and/or different test principle (e.g., indirect versus competitive), or a Western blot or a plasma HIV-1 RNA viral load.

- 3.1.3 The following laboratory tests within 14 days of study enrollment:
 - Hemoglobin \geq 10 g/dL (6.2 mmol/L)
 - Platelet count \geq 100,000/mm³ ($100 \times 10^9/L$)
 - ANC \geq 1500/mm³ ($1.5 \times 10^9/L$) (Participants receiving transfusion, erythropoietin, or myeloid growth factor support will be eligible for this study)
 - Creatinine clearance \geq 60 mL/min (1.00 mL/s) calculated by the Cockcroft-Gault equation for women
 - AST and ALT \leq 3 X ULN
 - Total bilirubin \leq 2 X ULN unless related to antiretroviral use (e.g., atazanavir and indinavir), then the direct bilirubin must be \leq 2 X ULN

- 3.1.4 Adults, 18 years of age or older. DOB and age should be determined based on best possible information or documentation available.
- 3.1.5 All patients must be prescribed combination antiretroviral therapy with the goal of virological suppression using an acceptable regimen that adheres to national guidelines for treatment of HIV infection. Further details can be found in [Section 4.2.3](#). Non-suppressed, treatment experienced patients, defined as patients with a viral load > 400 copies/mL who have been on antiretroviral therapy for more than 4 months can be enrolled if an alternative ART regimen is available that includes at least two ART drugs that, in the opinion of the site investigator, are expected to have activity based on genotypic testing (if available) and treatment history.
- 3.1.6 Ability to understand and the willingness to provide informed consent to participate.
- 3.1.7 ECOG performance status of ≤ 2 .
- 3.1.8 Participants of childbearing potential, defined as a sexually mature woman who: 1) has not undergone a hysterectomy or bilateral oophorectomy; or 2) has not been naturally postmenopausal for at least 24 consecutive months (i.e., has had menses at any time in the preceding 24 consecutive months), must have a negative urine or serum pregnancy test within 3 weeks prior to enrollment and agree to use an effective form of contraception (e.g., barrier contraception, highly effective hormonal contraception).
- 3.1.9 In the opinion of the investigator the protocol treatment is appropriate for the participant.
- 3.1.10 Life expectancy of greater than 12 months.

3.2 Exclusion Criteria

- 3.2.1 Participants who have undergone hysterectomy.
- 3.2.2 Acute active (such as tuberculosis or malaria), serious, uncontrolled infection. Participants with a CD4 count $\leq 50/\text{mm}^3$ ($0.05 \times 10^9/\text{L}$) will be excluded if they have had an opportunistic infection within the past 3 months, or if there is evidence of resistance to antiretroviral therapy (i.e., HIV viral load ≥ 400 copies/mL despite combination antiretroviral therapy for at least 4 months).
- 3.2.3 Prior invasive malignancy other than LACC diagnosed within the past 24 months, excluding anal intraepithelial neoplasia, non-melanoma skin carcinoma, or Kaposi's sarcoma that has not required systemic chemotherapy within the past 24 months.
- 3.2.4 Pregnancy or breast-feeding. Radiation therapy to the pelvis is contraindicated during any stage of pregnancy.

- 3.2.5 A medical or psychiatric illness that precludes ability to give informed consent or is likely to interfere with the ability to comply with the protocol stipulations.
- 3.2.6 Participants with circumstances that will not permit completion of the study or required follow-up. For instance, if travel to and from treatment site is an issue.
- 3.2.7 Participants with carcinoma of the cervical stump.
- 3.2.8 Participants with history of cardiovascular disease manifested as:
- History of myocardial infarction
 - Unstable angina
 - Currently taking medication for treatment of angina
 - History of coronary artery bypass surgery
 - New York Heart Association class 3 or 4 heart failure ([Appendix III](#))
- 3.2.9 Participants with enlarged para-aortic lymph node involvement on imaging that is suspicious for metastasis.

3.3 Number of Participants to be Enrolled

This study will enroll 45 participants, of whom we anticipate 38 will be evaluable. Once all sites are open for accrual, we anticipate the accrual rate to be 4-6 per month. Accrual is expected to take an estimated 24 months. All participants will have a minimum of 12 months of follow-up. We anticipate that at least 50% of recruited participants will be Stage 3 and 4A.

Accrual Targets					
Ethnic Category	Sex/Gender				
	Female		Male		Total
Hispanic or Latino	0	+	0	=	0
Not Hispanic or Latino	45	+	0	=	45
Ethnic Category: Total of all subjects	45 (A1)	+	0 (B1)	=	45 (C1)
Racial Category					
American Indian or Alaskan Native	0	+	0	=	0
Asian	0	+	0	=	0
Black or African American	45	+	0	=	45
Native Hawaiian or other Pacific Islander	0	+	0	=	0
White	0	+	0	=	0
Racial Category: Total of all subjects	45 (A2)	+	0 (B2)	=	45 (C2)
	(A1 = A2)		(B1 = B2)		(C1 = C2)

3.4 Recruitment Procedures

This study will be open at AMC African sites that have the capacity to deliver concomitant chemoradiotherapy as prescribed in this protocol. This includes weekly cisplatin at 40 mg/m² concomitant with radiotherapy (external beam and brachytherapy). Participating sites will need to have ART available for all enrolled participants that adheres to national guidelines for treatment of HIV infection. Sites that have this capacity will be approved by the leadership of this protocol. Participants will be either from primary clinics or from referrals that have HIV infection and incident LACC. Participants may originate from different health care settings.

3.5 Enrollment Procedures

This study will be available for enrollment at AMC core sites in Africa. Sites must have this protocol approved by their Institutional Review Board (IRB) or Independent Ethics Committee (IEC) and any relevant national and local authorities. Sites must also receive approval by the protocol leadership and register with the AMC Operations and Data Management Center (ODMC) before they may enroll participants. Protocol registration instructions and forms will be made available on the AMC Operations web site (www.amcoperations.com). Participating sites may not order study drug until protocol registration with the AMC ODMC is complete.

3.5.1 Registration for Screening

After an informed consent form has been signed by the participant, the participant must be registered for screening (AMC-081, Screening Segment) on-line via the AMC AdvantageEDCSM Internet Data Entry System. After successful registration into the screening segment, the participant will receive a nine-digit participant ID and will then enter the screening process. Participants will be enrolled on-line via the AMC Internet Data Entry System no more than 3 weeks prior to the initiation of treatment. Once the eligibility checklist is submitted, a system-generated confirmation will be sent to the site staff, AMC ODMC, and Protocol Chair upon successful registration.

Please reference the AMC-081 MOP for additional details regarding the required tests prior to enrollment in the screening segment.

If the on-line system is inaccessible for Screening Registration (Segment A), the site should notify the AMC ODMC via email at [contact] or via phone at [name] for further instructions. Please reference the AMC-081 MOP for additional instructions.

3.5.2 Enrollment

After the screening evaluations are completed and the participant is determined to be eligible the participating site will complete the protocol-specific eligibility checklist and enroll the participant into AMC-081 Treatment Segment (Segment B) on-line via the AMC AdvantageEDCSM Internet Data Entry System. The

participating site will ensure the participant meets all eligibility criteria prior to completing the protocol-specific eligibility checklist. Participants will be enrolled on-line via the AMC Internet Data Entry System no more than 1 week prior to the initiation of treatment (enrollment 1 day prior to or on the day of treatment is strongly encouraged). Once the eligibility checklist is submitted, a system-generated confirmation will be sent to the site staff, AMC ODMC, and Protocol Chair upon successful registration.

If the on-line system is inaccessible for Registration (Treatment Segment), the site should notify the AMC ODMC via email at [contact] or via phone at [name] for further instructions. If the AMC ODMC cannot be reached, please follow the manual randomization procedures detailed in the AMC-081 Manual of Procedures.

3.6 Required Pathology Material and Data

Local pathology must be performed according to local standard procedures to confirm the diagnosis of invasive squamous cell carcinoma, adenocarcinoma, or adenosquamous carcinoma of the uterine cervix. The local pathology review must be done prior to enrollment to confirm participant eligibility. Appropriate pathology reports from the participating institution are required to be maintained for source documentation.

A central pathology review will be performed according to [Appendix IV](#). The purpose of the central pathology review is to provide a consistent review and confirmation of the diagnosis and histology of cervical carcinoma for all study participants. This requirement applies to all cases, regardless of the country in which the subject is enrolled.

4.0 STUDY MODALITIES

To be eligible, participants with invasive squamous cell, adenocarcinoma, or adenosquamous carcinoma of the cervix must have undergone clinical staging by physicians according to FIGO staging criteria see [\(Appendix VI\)](#).

4.1 Staging

4.1.1 Clinical Staging

Participants must have a chest x-ray and a CT of the abdomen and pelvis with contrast. Stage should be assigned and documented as permitted under FIGO staging criteria. The para-aortic lymph node region must be negative for metastasis by CT with contrast.

Additional procedures, such as IVP, ultrasound, cystoscopy, proctoscopy, or barium enema may be performed at the discretion of the investigator.

4.1.2 All participants with cancer confined to the pelvis (Stages IB2, IIA, IIB, IIIB, IVA) will receive pelvic irradiation and concurrent cisplatin as outlined below.

4.2 Cancer Treatment Therapies

4.2.1 Radiation Therapy

See dose table below [\(Section 4.6\)](#) for details and appropriate fractionation schemes.

- 41.4-45.0 Gy/1.8 Gy per fraction/23-25 fractions/five weeks pelvic RT.
- 35-43.6 Gy intracavitary brachytherapy in one to two implants LDR or 18-28 Gy intracavitary brachytherapy in 2-4 fractions HDR.
- 5.40 - 9.00 Gy/1.8 Gy/3-5 fractions/3-5 days parametrial boost to involved parametria.
- Overall treatment time not to exceed eight weeks.

4.2.2 Chemotherapy

Cisplatin 40 mg/m² IV over 30-60 minutes given weekly on days 1, 8, 15, 22, 29 and 36 for a total of 6 weekly cycles.

4.2.3 Antiretroviral Therapy Regimen

4.2.3.1 All patients must be prescribed combination antiretroviral therapy with the goal of virological suppression using an acceptable regimen that adheres to national guidelines for treatment of HIV infection. Patients can already be on a regimen and remain on that regimen during treatment on this protocol. Subjects can begin ART on the day of enrolling in this study to meet eligibility criteria.

4.2.3.2 Although specific drugs will not be prohibited, when considering ART, please note the following:

- Cisplatin-associated neuropathy may be worsened by co-administration of didanosine (ddI) or stavudine (d4T)
- Anemia and neutropenia associated with cisplatin may be worsened by co-administration of Zidovudine (ZDV)
- Cisplatin-associated renal insufficiency may be worsened by co-administration of tenofovir

Whenever possible, co-administration of these antiretroviral agents should be avoided while study subjects are receiving cisplatin as part of this study. If co-administration is unavoidable and graded toxicities occur that require modification of the cisplatin dose, it is strongly recommended that, where available, the use of alternative antiretroviral drugs without overlapping toxicities, be considered before modifying the cisplatin dose.

4.3 Chemotherapy

4.3.1 Cisplatin (Platinol®-AQ –NSC #119875)

4.3.1.1 Formulation: Cisplatin is supplied as a sterile aqueous solution, each ml containing 1 mg cisplatin and 9 mg sodium chloride. Cisplatin is supplied in multidose vials containing either 50mg or 100mg of cisplatin.

NOTE: Aluminum reacts with cisplatin causing precipitation formation and loss of potency; therefore, needles or intravenous sets containing aluminum parts that may come in contact with the drug must not be used for the preparation or administration of cisplatin.

4.3.1.2 Storage: Store at 15 to 25°C. Do not refrigerate. Protect unopened container from light. The cisplatin remaining in the amber vial following initial entry is stable for 28 days protected from light or for 7 days under fluorescent room light.

4.3.1.3 Adverse effects: Leukopenia, thrombocytopenia, anemia, nausea, vomiting, nephrotoxicity, ototoxicity, peripheral neuropathy, electrolyte imbalance, hypocalcemia, hypomagnesemia, aminoglycoside ototoxicity, ocular toxicity, and allergic reactions.

Infrequent: Cardiac abnormalities, anorexia, elevated SGOT, rash, alopecia, and acute myeloid leukemia.

NOTE: Aminoglycoside antibiotics given before, with, or after cisplatin may potentiate renal toxicity and should be avoided whenever possible. Gentamicin ototoxicity is also potentiated by cisplatin and should be avoided whenever possible.

Severe renal toxicity can be largely avoided by induction of diuresis before, during and after treatment. Mild renal dysfunction is a common complication (10%) of chronic therapy and may require discontinuation of therapy if BUN \geq 30 mg/dL (10.7 mmol/L) or creatinine clearance $<$ 40 mL/min (0.67 mL/s) or creatinine $>$ 2.0 mg/dL (177 μ mol/L) develop. If serum creatinine is \geq 1.5 mg/dL (133 μ mol/L) on the planned treatment date, please see cisplatin dose modifications in [Section 6.2](#).

- 4.3.1.4 Supplier: Cisplatin will be purchased commercially and provided by the AMC.

*Refer to Package Insert for additional information.

4.4 Drug Orders, Transfers, Returns, and Accountability

The Investigator, or a responsible party designated by the Investigator, must maintain a careful record of the inventory and disposition of all drugs received using the NCI Drug Accountability Record Form (DARF) (available on the CTEP home page (<http://ctep.cancer.gov>) or by calling the Pharmaceutical Management Branch at [name]). The DARFs document the drug delivery date to the site, inventory at the site, use by each study participant, and disposal of the drug (if applicable). A site-specific accountability record, either manual or electronic, may be used if it includes all the information required on the NCI Investigational Drug Accountability Record and if the paper printout is identical to the NCI accountability record. A separate DARF is required for each protocol using the same agent. The investigator will ensure that the drugs are used only in accordance with this protocol.

Drug will be paid for by the AMC. Instructions for drug ordering/drug purchase will be provided to each clinical site by the AMC Operations and Data Management Center. All investigators prescribing study agent for an AMC study must have an active NCI-investigator registration.

4.5 Emergency Radiation Therapy to Stop Bleeding Prior to Treatment

In some cases of locally-advanced cervical cancer, particularly exophytic tumors, radiation therapy is required to stop bleeding emergently. Emergency RT is generally delivered in 3-5 fractions of 2-3 Gy per fraction. Patients who receive emergency radiation therapy to stop tumor bleeding either prior to enrollment or during screening will be allowed to proceed or be registered on this protocol as long as the other eligibility and ineligibility criteria are met. If a subject who is in either screening or pre-screening has received emergency radiation therapy, then definitive radiation therapy should be started as soon as possible so the total treatment time does not exceed 56 days.

4.6 Radiation Therapy Procedures

Radiation therapy (RT) must be started within 7 days of enrollment into the Treatment Segment (Segment B); CT scan of the pelvis is required for external RT field and block definition. If the participating site cannot perform CT simulation and yet has 3D planning software, a diagnostic CT scan with contrast should be available for treatment planning purposes.

Table of Doses

This protocol allows for external beam doses ranging from 41.4-45 Gy but still requires the treating physician to treat primary disease to 80-85 Gy target dose using the appropriate brachytherapy boost as outlined in the following two tables.

Table of Acceptable Combined External Beam and LDR Brachytherapy regimens

Ext. Beam Dose (1.8-2 Gy/fraction)*	LDR (1-2 implants)
41.4 Gy/23 fractions	38.6-43.6 Gy total
43.2 Gy/24 fractions	36.8-41.8 Gy total
45 Gy/25 fractions	35-40 Gy total

Table of Acceptable HDR Brachytherapy regimens

Number of Insertions	HDR Doses
2	9 Gy/fraction
3	7-8 Gy/fraction
4	6-7 Gy/fraction

*Any combination of EBRT and LDR/HDR dose regimen is acceptable. Higher dose per fraction should be considered only for larger, more advanced tumors. If a higher dose is being considered, the local Radiation Oncologist needs to consult with one of the Radiation Oncology PIs.

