4.6.1.2.5 Doses

Each HDR brachytherapy fraction will give 6-9 Gy/fraction to Point A. (Refer to [Appendix VIII](#) Description of points A, B and ICRU Bladder/Rectum). Each participant may be treated with up to four HDR implants with the HDR total dose ranging from 18-28 Gy (Total HDR dose) that is equivalent to an LDR delivered of 35-43.6 Gy depending on the total external beam dose given (Refer to [Appendix VII](#) HDR Brachytherapy).

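### Section 4.6: the dose-table footnote, read literally, lets external beam and LDR brachytherapy doses be combined to as little as 76.4 Gy or as much as 88.6 Gy, against a required 80-85 Gy, and the HDR route cannot be checked against that target

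*Combined protocol and SAP*

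**What the plan says.** Section 4.6 introduces its dose tables by allowing 41.4-45 Gy of external beam. It adds that the protocol "still requires the treating physician to treat primary disease to 80-85 Gy target dose", with the boost taken from the two tables that follow.

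- **LDR table.** Three rows, each pairing one external beam dose with its own LDR range. For example, "41.4 Gy/23 fractions" stands beside "38.6-43.6 Gy total".
- **HDR table.** Numbers of insertions and doses per fraction, with no external beam column.
- **Footnote.** Its mark sits on the external beam column of the LDR table, and it reads: "Any combination of EBRT and LDR/HDR dose regimen is acceptable". It also asks for consultation with a radiation oncology PI when a higher dose is considered.

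Other sections bear on the same dose:

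- Section 4.2.1 lists external beam 41.4-45.0 Gy, LDR 35-43.6 Gy and HDR 18-28 Gy as separate ranges and refers to the dose table.
- Section 4.6.1.2.1 repeats 35-43.6 Gy for LDR and says that the dose table serves to secure an adequate total.
- Section 4.6.1.2.5 treats 18-28 Gy HDR as equivalent to 35-43.6 Gy LDR, "depending on the total external beam dose given", and refers to Appendix VII.
- Section 4.6.1.1.1 defines the central dose as external beam dose plus intracavitary Point A dose. It classes a dose discrepancy of 6-10% as minor and above 10% as major.

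**The concern.** The LDR rows are built so that the boost makes up whatever the external beam dose leaves short of the target. A footnote that accepts any combination removes that link, and the section does not say whether the footnote or the 80-85 Gy requirement prevails. Two sites could read the same page differently, and each could point to text that supports it.

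Two things are at stake: the dose a participant receives relative to the protocol's own target, and the standard that dose QA applies. Under Section 4.6.6 and Appendix XII, every participant's radiotherapy is reviewed against the dose the protocol requires. If the protocol gives two answers, the reviewer has no single reference. For HDR the difficulty is different: the documents give no means of deciding whether a listed schedule reaches the target at all.

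**Working it through.** **Inputs.** The external beam doses and LDR ranges come from the LDR table in Section 4.6, as does the 80-85 Gy target. The rule of summation and the deviation thresholds come from Section 4.6.1.1.1.

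**Formula.** Central dose = external beam dose + LDR dose to Point A.

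**Step 1: reproduce the plan's figure from the table's own rows.**

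- 41.4 + 38.6 = 80.0; 41.4 + 43.6 = 85.0
- 43.2 + 36.8 = 80.0; 43.2 + 41.8 = 85.0
- 45 + 35 = 80.0; 45 + 40 = 85.0

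All three rows give exactly 80.0-85.0 Gy, so the pairing carries the target.

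**Step 2: the six cross-row pairings that the footnote admits if read literally.**

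| External beam (Gy) | LDR range (Gy) | Total (Gy) | Limit passed |
|---|---|---|---|
| 41.4 | 36.8-41.8 | 78.2-83.2 | lower |
| 41.4 | 35-40 | 76.4-81.4 | lower |
| 43.2 | 35-40 | 78.2-83.2 | lower |
| 43.2 | 38.6-43.6 | 81.8-86.8 | upper |
| 45 | 36.8-41.8 | 81.8-86.8 | upper |
| 45 | 38.6-43.6 | 83.6-88.6 | upper |

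Each range passes one limit, and each also overlaps 80-85 Gy. The unpaired ranges in Section 4.2.1 give the same extremes: 41.4 + 35 = 76.4 and 45 + 43.6 = 88.6.

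**Step 3: size against the deviation thresholds.**

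- From the nearest limit: (80 - 76.4)/80 = 3.6/80 = 4.5%; (88.6 - 85)/85 = 3.6/85 = 4.2%. Both are below 6%.
- From the midpoint, 82.5 Gy: 6.1/82.5 = 7.4% in either direction, which would be minor.

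The deviation rule refers to the dose specified in the protocol without saying which point of the 80-85 Gy range is the reference. Whether these totals are flagged depends on that choice.

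**Step 4: HDR.** Section 4.6.1.2.5 equates one range with another, conditional on the external dose. The HDR table has no external beam entry. Appendix VII covers vaginal surface dose, normal tissue tolerance, packing and imaging; its linear quadratic figures concern late-responding tissue, not tumour. No conversion from a listed HDR schedule to a contribution towards 80-85 Gy can be drawn from these texts, so no HDR total is calculated here.

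**The case against.** The strongest reply is that the section already shows which rule governs. The sentence before the tables says that the 80-85 Gy requirement still applies and is to be met from the tables, and Section 4.6.1.2.1 sends the reader to the table to secure the total. The LDR table's title presents each row as a combined regimen, so the footnote may mean only that any listed regimen, LDR or HDR, may be chosen. That reading is possible and would remove the LDR conflict. But the footnote does not say it, and nothing states an order of precedence. It would also leave HDR without a link to external dose.

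The consultation requirement is a partial safeguard. It may concern dose per fraction rather than total dose, and it does nothing at the low end.

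A reader might infer more than the documents support:

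- *That all footnote combinations miss the target.* The 76.4-88.6 Gy span contains 80-85 Gy; the same-row pairings meet it fully and the cross-row pairings in part.
- *That the lowest HDR total, 18 Gy, equals 35 Gy LDR and can be added to 41.4 Gy.* Section 4.6.1.2.5 gives no such point equivalence.
- *That off-target totals would be recorded as compliant.* Section 4.6.6 and Appendix XII provide for review of each participant's dose. What can be said is that the deviation threshold may not catch them.
- *That the primary completion measure is compromised.* Section 9.1.1 refers to completing the cisplatin/RT regimen and Section 11.1 to completing cisplatin. Neither ties completion to 80-85 Gy.

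**Conclusion.** The inconsistency is real as the text stands. For LDR, a literal reading of the footnote permits totals down to 76.4 Gy and up to 88.6 Gy, each 3.6 Gy beyond the nearest limit of the required range. That is modest by the protocol's own deviation scale, and for the same reason it may pass unflagged. The result rests on two assumptions: that the footnote is not confined to the same row, and that doses are summed as Section 4.6.1.1.1 prescribes. For HDR the conclusion is narrower: compliance with 80-85 Gy can be neither confirmed nor refuted from the documents. The point bears on dose safety and dose QA and is worth correcting. It does not show that any participant would be mis-dosed.

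**What to change.** The sponsor's radiation oncology chairs should reconcile the following and state which governs, both for treatment and for dose QA:

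1. the footnote in Section 4.6;
2. the paired LDR table;
3. the unpaired ranges in Sections 4.2.1 and 4.6.1.2.1;
4. the HDR table together with Section 4.6.1.2.5 and its reference to Appendix VII;
5. the 80-85 Gy requirement.

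The same clarification should name the reference dose for the 6% and 10% deviation thresholds. Which dose rule is right is for the chairs to decide, and none is proposed here.

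The cost is mainly wording in the footnote and its cross-references, made by amendment under Section 12.2. Sample size and the statistical analysis are unaffected.
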